6.2.3. Continued Access

The continued access period is defined in Section [6.2.1](#).

[Attachment 1](#) presents AE/SAE data collection and the necessary continued access follow-up visits, to occur after the decision is made to discontinue from the continued access period, or when the patient starts a new anticancer therapy, whichever happens first.

6.3. Discontinuations

The reason for and date of discontinuation from study treatment will be collected for all patients. The date of discontinuation (for any of the above reasons) from study treatment is to be reported on the case report form (CRF). Patients who discontinue from study treatment will have follow-up procedures performed as shown in the Study Schedule ([Attachment 1](#)).

If a patient withdraws informed consent, he or she must not be contacted unless he or she has explicitly provided permission and consent. Lilly may continue to use previously collected medical research data prior to the withdrawal consistent with the original authorization.

6.3.1. Discontinuation of Patients Inadvertently Enrolled

The criteria for enrollment must be followed explicitly. If the investigator site identifies a patient who did not meet enrollment criteria and who was inadvertently enrolled, the sponsor must be

notified. If the sponsor identifies a patient who did not meet enrollment criteria and who was inadvertently enrolled, the investigator site will be notified. A discussion must occur between the sponsor CRP or designee and the investigator to determine whether the patient may continue in the study, with or without investigational product. Inadvertently enrolled patients may be maintained in the study and on investigational product when the Lilly CRP or designee agrees with the investigator that it is medically appropriate for that patient. The patient may not continue on study treatment if the Lilly CRP or designee does not agree with the investigator's determination that it is medically appropriate for the patient to continue. The investigator must obtain documented approval from the Lilly CRP or designee to allow the inadvertently enrolled patient to continue in the study with or without investigational product.

6.3.2. Discontinuation of Patients from Study or Study Drug

Patients who are discontinued from the study drug(s) early will have follow-up procedures performed as shown in the Study Schedule ([Attachment 1](#)).

In addition, patients will be discontinued from the study drugs and/or from the study in the following circumstances:

- Enrollment in any other clinical trial involving an investigational product or enrollment in any other type of medical research judged not to be scientifically or medically compatible with this study.
- Investigator/Physician Decision
 - the investigator/physician decides that the patient should be discontinued from the study or study drug(s)
 - if the patient, for any reason, requires treatment with another therapeutic agent that has been demonstrated to be effective for treatment of the study indication, discontinuation from the study drug(s) occurs prior to introduction of the other agent
- Patient Decision
 - the patient or the patient's designee (for example, legal guardian) requests to be discontinued from the study or study drug
- Sponsor Decision
 - Lilly, in consultation with the collaborator, stops the study or stops the patient's participation in the study for medical, safety, regulatory, or other reasons consistent with applicable laws, regulations, and GCP
- The patient has confirmed evidence of progressive disease by RECIST v1.1. In the setting of disease progression, the patient will discontinue from study drug(s); however, the patient will continue to be followed on study. In the setting of unconfirmed/equivocal progression, the patient should remain on study treatment

until the next assessment period or up to 12 weeks after consultation with a Lilly physician. See Section 8.3.1.2 for additional details.

- The patient is noncompliant with study procedures and/or treatment (Section 7.6).
- The patient experiences unacceptable toxicity. Note: If the patient discontinues from 1 study drug, the patient should also discontinue from the other study drug.
- Patient has a dosing interruption of either study drug of >12 weeks.
- The patient becomes pregnant.

The reason for and date of discontinuation from study treatment will be collected for all patients. The date of discontinuation (for any of the above reasons) from study treatment is to be reported on the case report form (CRF). Patients who discontinue from study treatment will have follow-up procedures performed as shown in the Study Schedule ([Attachment 1](#)).

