Patients who have discontinued from combination treatment will enter the Post Discontinuation Follow-Up Period with visits at approximately 30, 60, and 90 days. If a patient has discontinued treatment for reasons other than disease progression, tumor assessments should continue every 8 weeks until confirmed disease progression occurs, initiation of a new anticancer therapy, the patient dies, or is lost to follow-up. Patients will be followed for survival at least every 12 weeks (± 7 days) until death or study completion. This follow-up may occur through a phone call, email, or visit by the patient or the patient's caretaker.

Refer to [Attachment 1](#) for the Study Schedule.

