7.5. Concomitant Therapy

No other therapy, including routine use of growth factors or experimental medications (for example, immunotherapy or other not approved medication) will be permitted while the patients are on the study. Growth factors and erythropoietin are allowed per American Society of

Clinical Oncology or National Comprehensive Cancer Network guidelines. Granulocyte colony-stimulating factors must be discontinued at least 24 hours prior to the start of the next cycle of treatment. Transfusions are permitted. Patients may receive prophylactic steroids (such as, prednisolone, methylprednisolone or dexamethasone; see below for limits) to prevent transfusion reactions.

Any concurrent antineoplastic therapy (ie, chemotherapy, hormonal therapy, immunotherapy, extensive, nonpalliative radiation therapy, or standard or investigational agents for treatment of pancreatic cancer) will not be allowed unless outlined elsewhere. Any disease progression requiring other forms of specific antitumor therapy will necessitate early discontinuation from the study. Appropriate documentation for all forms of premedications, supportive care, and concomitant medications must be captured on the CRF. Replacement hormonal therapy initiated before study entry will be allowed.

Immunosuppressive medications will not be allowed including, but not limited to systemic corticosteroids at doses exceeding 10 mg/day of prednisone or equivalent, methotrexate, azathioprine, and tumor necrosis factor- α blockers. Use of immunosuppressive medications for the management of investigational product-related AEs, in patients with contrast allergies or for treatment of nonautoimmune conditions (eg, delayed-type hypersensitivity reaction caused by a contact allergen) is acceptable. Patients are also permitted the use of topical, ocular, intra-articular, intranasal, and inhalational corticosteroids (with minimal systemic absorption) unless outlined elsewhere. Live attenuated vaccines within 30 days of durvalumab dosing are not permitted (ie, 30 days prior to the first dose, during treatment with durvalumab and for 30 days post discontinuation of durvalumab). Inactivated vaccines, such as the injectable influenza vaccine, are permitted. Seasonal influenza vaccines for injection are generally killed virus vaccines and are allowed; however, intranasal influenza vaccines (eg, FluMist[®]) are live attenuated vaccines and are not allowed (see Section 6.1.3).

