8.1.2.2.3. Follow-Up Visit

All AEs and SAEs, regardless of relatedness to study drug(s) or protocol procedures, occurring during the 30-day, 60-day, and 90-day safety follow-ups occurring after last dose of combination treatment must be reported to Lilly or its designee ([Attachment 1](#)).

Following the 30-, 60-, and 90-day follow-up assessments, patients who discontinue from study treatment for progressive disease will be followed only for survival, unless there is an ongoing AE or SAE that is possibly related to study drug or protocol procedures. In this instance, the patient should be followed in subsequent follow-up visits until the event is resolved, the event is no longer considered to be drug-related, the event becomes stable or returns to baseline, a new treatment is initiated for the patient, or the patient dies or is lost to follow-up. For patients who have discontinued study treatment for reasons other than progressive disease, these patients will be followed for survival, progression-free survival (PFS), time and duration of response, and best overall response (BOR), unless they have started another treatment. In that case, the patient will only be followed for survival. Patients with an ongoing AE or SAE that is possibly related to

study drug or protocol procedures will be followed until the event is resolved, unless a new treatment is started.

If it is deemed to be in the best interest of the patient to start a new anticancer treatment prior to the scheduled end of the 90-day follow-up visit, the follow-up visit duration may be shortened. In this case, the follow-up assessments should be completed prior to the initiation of the new therapy.

After the 90-day follow-up visit, AEs are not required to be reported unless the investigator feels the AEs were related to either study drug or a protocol procedure. If an investigator becomes aware of an SAE believed to be related to protocol procedures or study drug, the investigator should report the SAE to the sponsor, and the SAE will be entered in the Lilly Safety System.

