#### **6.13.1. Efficacy Analysis Variables (RECIST v.1.1)**

Definition of efficacy analysis variables are listed alphabetically.

**Disease Control Rate** is defined as the proportion of treated patients achieving a best overall response of complete response (CR), partial response (PR), or stable disease (SD) per RECIST v.1.1. Patients who do not have any postbaseline tumor response assessments for any reason are considered non-responders and are included in the denominator when calculating the response rate.

**Note.** Best overall response is the best response recorded from the start of treatment until disease progression, in the order of CR, PR, SD, PD, and NE.

**Duration of Response** is defined from the date of first documented CR or PR that is subsequently confirmed (responder) to the date of objective progression or the date of death due to any cause, whichever is earlier. If a responder is not known to have died or have objective progression, then the patient will be censored at the date of last evaluable tumor assessment.

**Objective response rate** is defined as the proportion of treated patients achieving a best overall response of PR or CR per RECIST v.1.1. Patients who do not have any postbaseline tumor response assessments for any reason are considered non-evaluable and are included in the denominator when calculating the response rate.

**Overall survival** is defined as time from the date of first treatment to the date of death from any cause. For each patient who is not known to have died as of the data-inclusion cut-off date for a particular analysis, OS will be censored for that analysis at the date of last contact prior to the data-inclusion cut-off date (contacts considered in the determination of last contact date include AE date, lesion assessment date, visit date, and last known alive date).

**Progression-free survival** is defined as the time from the date of first treatment until the date of radiographic documentation of progression (as defined by RECIST v. 1.1) based on investigator assessment or the date of death due to any cause, whichever is earlier.

**Time-to-response** is the time from the date of first study treatment until the first evidence of a confirmed CR or PR.

[Table CXAD.6.2](#) lists rules for determining date of progression or censor for PFS. The censoring is taken in the following order:

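### Protocol Section 7.5 can be read as ending study participation when progression needs other antitumor therapy, which contradicts the survival follow-up written in the rest of the protocol

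*Protocol*

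**What the plan says.** Protocol Section 6.3.2 covers confirmed progression: "In the setting of disease progression, the patient will discontinue from study drug(s); however, the patient will continue to be followed on study". The same section covers a patient who needs another effective agent, and it speaks only of the drugs: "discontinuation from the study drug(s) occurs prior to introduction of the other agent".

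Protocol Section 7.5, on concomitant therapy, says: "Any disease progression requiring other forms of specific antitumor therapy will necessitate early discontinuation from the study".

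The follow-up provisions are these:

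- Protocol Section 6.2: "Patients will be followed for survival at least every 12 weeks (± 7 days) until death or study completion". It makes no exception for new therapy.
- Protocol Section 6.2.2: long-term follow-up runs from the end of the 90-day visit until death or end of trial.
- Protocol Section 8.1.2.2.3: after the 30-, 60- and 90-day assessments, "patients who discontinue from study treatment for progressive disease will be followed only for survival", apart from ongoing related events. Patients who stopped for another reason and then start a different treatment also stay in survival follow-up.
- Protocol Attachment 1: one row collects survival status and later anticancer therapy together, at the three short-term visits and in long-term follow-up.

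SAP Section 6.13.1 counts death from any cause. For a patient not known to have died, "OS will be censored for that analysis at the date of last contact prior to the data-inclusion cut-off date".

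**The concern.** Sections 6.3.2 and 7.5 both apply to the patient who progresses and goes on to another treatment, and they cannot both be followed. One keeps the patient on study and the other removes the patient from it.

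Overall survival is one of the variables that serve the secondary antitumor objective, and each expansion arm has only about 15 patients. If contact ended when new therapy began, the censoring would depend on having progressed and on being fit enough for more treatment. Kaplan-Meier estimation assumes that censoring carries no such information. The patient could also be entered as having discontinued the study in the SAP Section 6.4 disposition summary, although Section 6.3.2 says that the patient remains in follow-up.

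**Working it through.** **Does leaving the study mean something different from leaving treatment?** Yes, in four places:

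- Protocol Section 6.2.2: patients already in long-term follow-up when continued access begins leave the study. They are off drug, so this can only mean that follow-up ends.
- Protocol Table CXAD.8.1: patients no longer on study have their own row, with much narrower reporting.
- SAP Section 6.4: reasons for stopping treatment and for stopping the study are summarized separately.
- SAP Section 6.17: the registry participant flow uses study discontinuation, not treatment discontinuation.

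A site is therefore entitled to take the Section 7.5 wording at face value.

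**What happens to overall survival?**

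1. Under Sections 6.2, 6.2.2, 6.3.2 and 8.1.2.2.3 and Attachment 1, contact continues after progression and after new therapy. Deaths are recorded, and the error from this source is zero.
2. Under Section 7.5 read literally, contact may stop at new therapy. The SAP rule then places the censoring date at about that time.

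**How large could case 2 be?** The plan gives no survival median, rate, event count or power to reproduce. The following is an illustration in which every input is assumed:

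- Median time to progression 2 or 4 months; hazard of death before progression 0.02 or 0.05 per month.
- Median survival after progression 3 or 6 months, with hazard = ln 2 / median.
- 30% or 60% of progressors receive other therapy, with a post-progression hazard multiplied by 1.0 or 0.6.
- Cut-off at 12 months; 2 × 2 × 2 × 2 × 2 = 32 settings; 200,000 simulated patients per setting.

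Full follow-up uses time = min(survival, 12), with an event if survival ≤ 12. Literal Section 7.5 censors each progressor given other therapy at min(progression time, 12). That simplifies the start of new therapy and assumes that every such patient is lost. Selected settings:

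| Progression median | Post-progression median | Pre-progression hazard | Multiplier | Given other therapy | 6-month survival, full → literal | Median, full → literal (months) | Deaths kept |
|---|---|---|---|---|---|---|---|
| 4 | 3 | 0.02 | 1.0 | 30% | 0.61 → 0.66 | 7.5 → 8.4 | 74% |
| 4 | 3 | 0.02 | 1.0 | 60% | 0.61 → 0.73 | 7.5 → 10.2 | 48% |
| 2 | 3 | 0.02 | 1.0 | 60% | 0.46 → 0.59 | 5.6 → 7.1 | 44% |
| 2 | 6 | 0.05 | 0.6 | 60% | 0.65 → 0.64 | 9.2 → 8.4 | 59% |
| 4 | 6 | 0.05 | 0.6 | 30% | 0.67 → 0.66 | 9.4 → 9.2 | 84% |

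Across all 32 settings, 44% to 84% of deaths are kept. With multiplier 1.0, 6-month survival is overstated by about 1 to 13 points. With multiplier 0.6 the error runs from about -1 to +7 points. Progression starts a period of higher hazard, so censoring there tends to raise the curve. If those removed are the fitter progressors, the effect shrinks and can reverse.

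For scale, Protocol Table CXAD.10.1 gives a 95% interval of 0.32 to 0.84 for 9 of 15, a width of 0.84 - 0.32 = 0.52. That is a binomial proportion rather than a Kaplan-Meier estimate, but it shows how imprecise an arm of 15 already is.

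**The case against.** The strongest answer is that the protocol's intent is plain. The sections that govern follow-up all continue survival contact. Section 6.3.2 itself stops only the drugs when another agent is needed. Attachment 1 records later anticancer therapy during follow-up, which presupposes that such patients are still there. Section 7.5 governs concomitant treatment, and its phrase probably means leaving treatment. All of this stands. It shows that Section 7.5 is the outlier, but it does not remove the contradictory sentence.

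Four stronger readings are tempting, and the documents do not support them:

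- *Deaths are lost and survival is censored because of progression.* Neither progression nor new therapy is a censoring reason in SAP Section 6.13.1, and the follow-up sections require contact until death or study completion. Loss needs a site to put Section 7.5 above all of these.
- *Section 6.3.2 itself removes a progressor who joins another trial.* Its list opens with "patients will be discontinued from the study drugs and/or from the study in the following circumstances", and for a patient already off drug it may seem that only the study is left. But the and/or wording permits stopping drug alone, and the section sends patients who stop drug early to the Attachment 1 follow-up. The text leaves this case unstated; it does not order removal.
- *The conflict ends follow-up of ongoing related adverse events.* Sections 8.1.1 and 8.1.2.2.3 already allow that follow-up to end when a new treatment starts, so Section 7.5 is not the cause.
- *Disposition is broadly distorted.* SAP Section 6.4 defines completion as one cycle in Phase 1a (or stopping earlier for a dose-limiting toxicity) and two cycles in Phase 1b. The first on-treatment scan falls just before Cycle 3, so many progressors will already count as completers. The effect is limited mainly to recorded reasons for study discontinuation.

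**Conclusion.** The contradiction is real, and the Section 7.5 sentence is wrong as written. Its consequence is conditional. If sites follow the other sections, no deaths are lost for this reason. If a site follows Section 7.5 literally, overall survival can be censored in a way linked to prognosis, and the patient can be misclassified in the disposition summary.

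The size cannot be derived from the documents. The simulated ranges rest wholly on assumed inputs and on complete loss of contact, and the sign of the error is not fixed. All analyses are descriptive, with no p-values (Protocol Section 10.1), so no error rate or sample size is affected. This is a wording inconsistency of minor to moderate weight. It is worth correcting because deaths missed at a site may not be recoverable later.

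**What to change.** Reconcile the Section 7.5 sentence with Protocol Sections 6.2, 6.3.2 and 8.1.2.2.3 so that it does not end study participation. Add one statement that survival follow-up under Section 6.2 continues after new anticancer therapy or entry into another trial, unless the patient withdraws consent to be contacted (Section 6.3).

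Leave every treatment-stopping criterion as it is, and make no change to adverse event follow-up on this account. The Section 6.3.2 list need not be re-sorted. Doing so would reopen treatment beyond progression (Sections 6.2 and 8.3.1.2) and removal for pregnancy (Section 8.1.2), which are separate matters.

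The cost is a few sentences in the next amendment and a note to sites. Survival contacts by phone, email or visit are already planned, so no procedures are added.

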6.3.3. Discontinuation of Study Sites

Study site participation may be discontinued if Lilly, the investigator, or the ethical review board (ERB) of the study site judges it necessary for any scientific, medical, safety, regulatory, ethical, or other reasons consistent with applicable laws, regulations, and GCP.

6.3.4. Discontinuation of the Study

The study will be discontinued if Lilly, while considering the rights, safety, and well-being of the patient(s), judges it necessary for any scientific, medical, safety, regulatory, ethical, or other reasons consistent with applicable laws, regulations, and GCP.

7. Treatment

7.1. Materials and Supplies

7.1.1. LY2510924

LY2510924 for Injection, 20mg/mL will be supplied as a single use sterile clear solution formulation in 2 mL glass vials. Each vial contains 1.15 mL of a 20 mg/mL LY2510924 solution. The excess solution is supplied to facilitate the withdrawal of a 20-mg unit dose. One mL will be drawn from each vial to deliver 20 mg of LY2510924. The LY2510924 drug product contains no antimicrobial preservative.

The drug product is composed of LY2510924 and the inactive ingredients sodium citrate dihydrate, citric acid monohydrate, sodium chloride, sterile water for injection with sodium hydroxide and/or hydrochloric acid used if necessary for pH adjustment. Vials of LY2510924 for Injection, 20mg/mL, must be stored refrigerated (2°C to 8°C).

Clinical study materials will be labeled according to the country's regulatory requirements.

7.1.2. Durvalumab (MEDI4736)

Durvalumab (MEDI4736) will be supplied as a 500-mg vial solution for infusion. The solution contains 50 mg/mL durvalumab, 26 mM histidine/histidine-hydrochloride, 275 mM trehalose dihydrate, and 0.02% weight/volume (w/v) polysorbate 80; it has a pH of 6.0. The nominal fill volume is 10 mL. Investigational product vials are stored at 2°C to 8°C (36°F to 46°F) and must not be frozen.

The dose of durvalumab for administration must be prepared by the Investigator's or site's designated study manager using aseptic technique. Total time from needle puncture of the durvalumab vial to the start of administration should not exceed:

- 24 hours at 2°C to 8°C (36°F to 46°F)
- 4 hours at room temperature

If in-use storage time exceeds these limits, a new dose must be prepared from new vials. Infusion solutions must be allowed to equilibrate to room temperature prior to commencement of administration. Durvalumab does not contain preservatives and any unused portion must be discarded.

Clinical study materials will be labeled according to the country's regulatory requirements.

